#### Data Transfer:

We have both a PHSA networked computer in our lab (where data is stored) and UBC networked computers in our lab and with our statistician (both at BC Women's Hospital).

In order to analyze the data using sophisticated statistical analysis software it is necessary to transfer coded data temporarily from the PHSA networked computer to a UBC networked computer to complete the analysis. The data storage described above will not change. Identifiable information will never be transferred from the secure PHSA network.

A) Coded information only. No identifying information will be transferred.

B) The data will remain within the study team.

C) The data will be transferred for use on a UBC networked computer for data analysis but the data will not be stored on the UBC computer. All data will continue to be stored on the secure PHSA network.

D) Data will be transferred to an encrypted/password protected USB stick for use on a UBC networked computer temporarily for analysis. The data will always be returned to the PHSA network for storage. The UBC computers are housed in the same physical location as the PHSA computers.

---

#### DATA ANALYSIS

---

The data collected from the 30 case participants was used to execute a power analysis to determine the total sample size required for the study. With power=0.80 and  $\alpha=0.05$  two tailed, a sample size of 126 case participants was needed.

For the cases, statistical analysis following collection of the data will be done using a Spearman Correlation determine if there is significant association between PPT and the primary outcome (deep dyspareunia) and secondary outcomes (e.g. non-sexual pain). Mann-Whitney association may be done for the bladder and pelvic floor variables to determine if they are significantly associated with PPT. Multiple Variable Regression may be done using variables significantly associated to determine if they are independently associated, independent of possible confounders. Comparison of PPT between cases and controls will also be done, but the main reason for the controls is for troubleshooting of the QST.

---

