**Research Hypothesizes:**

**Primary Hypothesis:** Central sensitization (measured by pain-pressure threshold) is associated with an increased severity of deep dyspareunia, as well as a tenderness of the bladder and pelvic floor, in women with endometriosis.

**Secondary Hypothesis:** Women with endometriosis will have a great central sensitization (indicated by a lower pain-pressure threshold) than women without endometriosis.

**Outcome:** Central sensitization (lower pain-pressure threshold) will be strongly and positively correlated with the severity of deep dyspareunia, and will also be associated with bladder and pelvic floor tenderness.

---

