#### Procedures for Data Collection (on Test day)

#### **Questionnaire:**

#### Case and Control:

- Data will be collected during a scheduled appointment with [name] or her delegate. The research visit will take approximately one hour of the participant's time (not including travel time to and from the site). The visit will take place in a BC Women's Health Centre private room (4th floor of the Shaughnessy building at the BC Women's Hospital). Data collected will include an online questionnaire containing: today's date, score of sexual and non-sexual pains, first day of last menstrual period, any changes in medication since their last visit to BC Women's Health Centre, current hormonal suppression, date of last physician appointment, menstrual cycle data, last time they have had sexual intercourse and how many times have they had sexual intercourse in the last one month. The pelvic pain questions asked on this online questionnaire are modified from the Brief Pain Inventory Short Form. This questionnaire will be filled out on REDCap online using a desktop computer in the room.
- The testing room will be maintained at a temperature between 20 and 25 degrees Celsius, with no fans or open windows (may use a white noise machine), and no stressful stimuli (e.g., no loud noises or blinking lights).
- As the participant completes the online questionnaire, [name] or her delegate will set up the Algometer and calibrate the force sensing resistor (FSR). [name] or her delegate will answer any questions.

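### The only stated entry rule for the optional adjusted regression is bivariate significance, and no confounder, model outcome or role for tenderness is fixed, so the adjusted PPT association may be biased

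*Combined protocol and SAP*

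**What the plan says.** The DATA ANALYSIS section of the combined protocol and SAP commits to unadjusted Spearman correlations, within cases, of PPT with deep dyspareunia and with the secondary outcomes. It then makes two steps optional. The first concerns tenderness: "Mann-Whitney association may be done for the bladder and pelvic floor variables to determine if they are significantly associated with PPT". The second is the only adjusted analysis in the document: "Multiple Variable Regression may be done using variables significantly associated to determine if they are independently associated, independent of possible confounders".

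Other sections bear on what could enter that model:

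- Background Literature says that tenderness of the bladder and pelvic floor may be a marker of central sensitization, and that this link still needs confirming.
- The primary hypothesis (Research Hypothesizes) ties central sensitization to deep dyspareunia "as well as a tenderness of the bladder and pelvic floor". Secondary objective 2 asks about tenderness and central sensitization directly.
- Design makes deep dyspareunia the primary outcome and PPT the main independent variable. The Research Question under Research Objectives puts the direction the other way round, from dyspareunia to PPT.
- The test-day questionnaire records "current hormonal suppression, date of last physician appointment, menstrual cycle data", among other items. Data Linking says that all registry data will be linked but does not list the variables.

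**The concern.** This is an observational study, so only the regression can support a statement that PPT and deep dyspareunia are associated independently of other factors. Selecting terms by significance serves that purpose badly in two ways.

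First, a confounder does its damage through the product of its links with exposure and outcome. A test of one of those links in 126 women will often miss a modest one, and the confounder is then left out.

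Second, the variables tested just before the regression sentence include tenderness. If tenderness is a consequence or marker of sensitization, placing it beside PPT removes part of the association being studied. The better the tenderness hypothesis holds, the more likely tenderness is to pass the screen.

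Because the covariates and even the dependent variable are open, the choice would be made after the results are seen.

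**Working it through.** **Inputs from the plan.** There are 126 cases, with power 0.80 and two-sided alpha 0.05: "two tailed, a sample size of 126 case participants was needed". The effect size is not stated; the plan says only "The data collected from the 30 case participants was used to execute a power analysis". No confounder strength is given anywhere, so all strengths below are assumptions.

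**The plan's own figure.** N = ((1.960 + 0.842)/atanh(r))² + 3. Solving for r at N = 126 gives r = tanh(2.802/√123) = 0.247. Allowing for the Spearman variance (factor 1.06) gives 0.254. With r = 0.25 the formula gives 124. So 126 cannot be reproduced forward, but it corresponds to a correlation near 0.25, which sets the scale for what follows.

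**Step 1: chance that a covariate passes p < 0.05.** This is approximately Φ(atanh(r)·√123 − 1.96).

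| True correlation with the screening variable | Flagged | Dropped |
|---|---|---|
| 0.10 | 20% | 80% |
| 0.15 | 39% | 61% |
| 0.20 | 61% | 39% |
| 0.25 | 81% | 19% |
| 0.30 | 93% | 7% |

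**Step 2: effect on false positives.** Simulation with n = 126, 4,000 replicates, ordinary least squares and no true PPT effect. With four confounders of 0.3 to PPT and 0.15 to the outcome, the crude confounded correlation is 4 × 0.3 × 0.15 = 0.18.

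| Four confounders | Rejection rate |
|---|---|
| 0.3 to PPT, 0.15 to outcome; screen on outcome | about 13% |
| Same; screen on PPT | about 5% |
| Same; must pass both | 13.6% |
| Same; all four forced in | 4% to 5% |
| Paths swapped (0.15 to PPT, 0.3 to outcome); screen on PPT | 12.5% |

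The screen does harm when it looks at the weaker of the two links, because each confounder is then kept only 39% of the time.

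Milder settings did less. One confounder at 0.1 to 0.3 on both links gave rejection of 4.5% to 5.2% and a mean standardised PPT estimate of 0.002 to 0.011, where the truth is 0. Three such confounders gave 5.0% to 6.4% and 0.012 to 0.031. With a true coefficient of 0.247 and three confounders at 0.2, the mean screened estimate was 0.275 (screen on PPT) or 0.256 (screen on outcome).

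**Step 3: admitting a consequence of sensitization.** Let S be sensitization, and let PPT = −(l·S + noise), tenderness M = m·S + noise and dyspareunia Y = c·S + d·M + noise, all standardised. Then r(PPT,Y) = −l(c + d·m), r(PPT,M) = −l·m and r(M,Y) = c·m + d. The adjusted coefficient is [r(PPT,Y) − r(PPT,M)·r(M,Y)]/[1 − r(PPT,M)²].

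- Moderate mediator (l 0.6, m 0.5, d 0.3, c 0.26): (−0.246 + 0.30 × 0.43)/(1 − 0.09) = −0.13, a loss of 48%.
- Strong mediator (l 0.6, m 0.7, d 0.3, c 0.20): (−0.246 + 0.42 × 0.44)/(1 − 0.1764) = −0.07, a loss of 70%.
- Marker with no effect of its own (l 0.7, m 0.5, d 0, c 0.353): (−0.247 + 0.35 × 0.1765)/(1 − 0.1225) = −0.21, a loss of 15%.

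**The case against.** The best defence is that the sentence can be read differently. The terms that passed the bivariate tests may be the study variables under examination, with a separate set of confounders adjusted for and not screened. A reader might infer that hormonal suppression or menstrual phase enters only if significant, but the text does not say so. That stands, and it limits the firm finding to an unspecified model. It does not rescue the plan, since no separate set is named.

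The sizes also depend on choices the plan does not make. Every bivariate test it describes is against PPT, and a PPT screen gave about 5% in one four-confounder setting and 12.5% in the other. So 13% cannot be quoted as the expected error rate.

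Two stronger readings fail on the documents:

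- A reader might class the other pain scores and EHP-30 as consequences of sensitization. The plan calls only tenderness a possible marker, and lists the others as secondary outcomes or correlates.
- A reader might want tenderness barred from all modelling. The plan asks about tenderness in its own right, so that would discard one of its questions.

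It is also true that the regression is optional and that the Spearman analysis does not depend on it. But an optional, open model makes selective reporting easier.

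**Conclusion.** The concern holds as a gap in the adjusted analysis and should be fixed. The only entry rule written down is bivariate significance. With 126 cases, such a rule misses a covariate correlated 0.15 in 61% of samples and one correlated 0.20 in 39%. It can also let in tenderness, which is the larger risk in the settings tried: a loss of 15% to 70% of the PPT coefficient, against a mean bias of about 0.01 to 0.03 from one to three dropped confounders of equal strength on both links. With four confounders of unequal links, false positives ran from about 5% to 13%.

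All of this rests on assumed strengths and on the natural reading of one sentence. A reader might infer that the adjusted result will be biased or that its intervals will be too narrow. The documents support only that it may be biased, and interval coverage was not calculated. Nor is the primary result at risk from this rule, because the Spearman correlation is unadjusted.

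**What to change.** Replace the regression sentence in DATA ANALYSIS with:

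> Deep dyspareunia severity will be regressed on PPT, adjusted for a pre-specified set of confounders chosen on subject-matter grounds and retained regardless of significance: current hormonal suppression and menstrual phase from the test-day questionnaire, and age, BMI and disease state if confirmed to be in the linked registry. The main model will exclude bladder and pelvic floor tenderness. A second model adding them will be reported and labelled as adjusting for possible markers of central sensitization. The association of tenderness with PPT will be analysed separately, with the same confounder set.

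This turns an optional model into a planned one and follows the Design section on which variable is the outcome. Before finalising it, the sponsor should confirm the registry fields. The protocol mentions height and weight only for controls, and does not show that age and BMI are recorded for cases in an analysable form.

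The cost is analysis wording and about 5 to 7 degrees of freedom out of 126. At 7, the standard error grows by about √(124/117) − 1 = 3%, before allowing for correlation between PPT and the confounders.

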#### ETHICAL CONSIDERATIONS

---

Risk to participants: By participating in this study the participants will experience pain or discomfort due to the measurement of PPT. However, the test inflicts the least amount of pain, as the test is stopped immediately once the participant feels any discomfort. Additional risks associated with completing very personal questions and undergoing QST due to the case participant's possible history of chronic pain includes: psychological, emotional or physical discomfort. If any additional risks are discovered, these risks will be disclosed immediately and new consent forms will be created and sent to participants. If any adverse reactions were to occur, the participant will be triaged by the clinic nurse at the BC Women's Health Centre, and assessed by a physician if required. Another risk to participants is accidental release of data. All precautions are being taken to assure that this does not occur (e.g. limited access, limited data transfer, de-identifying the data, etc.).

Risk to investigators: There are no known risks to investigators. Any risks that are discovered will be disclosed immediately to the study PI.

Benefit: There are no direct benefits to the health care of the participants. Our Centre sends regular newsletter to participants, to update them on research findings.

Informed Consent Process: The patients will be given a minimum of 24 hours to decide whether or not they want to participate. [name] or her delegate will explain the consent form in detail to the patients and will answer any questions they may have. If deciding to participate, the patients will consent to the study in-person, as well as on REDCap for the control participants. .

Privacy and Confidentiality: As outlined in the procedures, each participant record on REDCap is assigned a unique study ID number that can only be decrypted by a linking excel file separately stored on the PHSA restricted access secure O: drive. This linking spreadsheet is encrypted and kept in a folder that can only be accessed by select members of the clinical and research team. Care will be taken that unique study IDs and identifiers will not appear together anywhere other than the master file.

Within REDCap, each record contains an embedded email for the purpose of sending automated invitations with a link to initial pre-visit questionnaire (controls only), consent form (controls only) and post-appointment day daily surveys (cases only).

No participant data will be stored on the test laptop. The PPT data will be written down on a paper copy with the participant's unique study ID at the top to link them to their REDCap data. The paper copy will be entered into an encrypted file on a PHSA secure computer. All paper data will be placed in a confidential file box and shredded as per hospital policy. If needed, computer files will be deleted according to UBC policy 85.

The data from the survey can be viewed by [name] or her delegate via REDCap; therefore, there is no risk of disclosure of information by unsecured email servers.

All researchers in this study have been trained in the proper protocol for privacy and confidentiality, including completion of the Tri-Council Policy Statement: Ethical conduct for Research Involving Humans (TCPS-2 CORE) and a Privacy and Confidentiality course provided by PHSA.

---

#### **DATA STORAGE/ DATA HANDLING**

---

The online questionnaires, daily surveys and control consent form will be housed on the Research Electronic Data Capture (REDCap) platform located at the Child and Family Research Institute (CFRI) on the BC Children's and BC Women's Hospital and Health Centre campus.

The actual data for each database is stored on a private, relational MySQL Database at the data center which is located on-site at CFRI. CFRI IT is responsible for creating REDCap database backups and these backups are stored at Iron Mountain Canada, ensuring that all data and backups are stored in Canada. The CFRI Clinical Research Support Unit (CRSU) stores study data in a secure, firewall protected server with only the https ports available to internet. There is a web application server that is the only gate to connect to the Database server, where the information is stored.

The Database Management System uses a web server that employs Secure Socket Layer (SSL) technology for the secure transfer of data between a client computer and the server. The actual data center is a physical secured and protected area. Physical access to this room is extremely limited and is controlled by CFRI IT and security personnel through a process of authorizing and granting access linked to identification cards. A record of access rights is recoded and kept by both the CRFI IT and security personnel. The data center is also patrolled by on-site security personnel, monitored by surveillance cameras, and protected by a fire suppression system.

PPT measurements will be stored in an encrypted file on the O: drive within the PHSA network. Only investigators in this study and delegates will have access to this file. No data will be stored on the test laptop or the UBC computer.

---

#### DISSEMINATION OF RESULTS

---

Results from the study will be published in academic and non-academic journals, presented at conferences or events and made available online (e.g. departmental or individual websites). Participants will be notified of the results of the study through our research newsletter.

[figure not shown]
---

## Appendix A

**Note:** Researcher is [name] or her delegate

## Appendix B

**Note:** Researcher is [name] or her delegate

## Appendix C

| Question   | Range of Responses  |
|--|---|
| Today's Date   |   |
| What was your average level of pelvic pain in the last 24 hours?                             | 0= no pain, 1, 2, 3, 4, 5, 6, 7, 8, 9, 10= worst pain imaginable                                  |
| Have you experienced menstrual bleeding in the last 24 hours?                                | 0= none, 1=spotting, 2= bleeding  |
| In the last 24 hours, how painful was deep penetration during sexual intercourse?            | Not applicable (no intercourse), 0= no pain, 1, 2, 3, 4, 5, 6, 7, 8, 9, 10= worst pain imaginable |
| In the last 24 hours, how painful was initial penetration (entry) during sexual intercourse? | Not applicable (no intercourse), 0= no pain, 1, 2, 3, 4, 5, 6, 7, 8, 9, 10= worst pain imaginable |

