## **BACKGROUND LITERATURE**

---

Endometriosis results from the presence of endometrial cells growing abnormally outside the uterus and affects approximately 10% of reproductive-aged females. Endometriosis can be associated with various types of pain such as: dysmenorrhea (painful cramps with menses), deep dyspareunia (pelvic pain with deep intercourse), dyschezia (painful bowel movements) and chronic pelvic pain. Few studies have explored the association between endometriosis and deep dyspareunia resulting in a limited understanding of how to treat deep dyspareunia. Deep dyspareunia is defined as pelvic pain with deep sexual intercourse and occurs in 50% of women with endometriosis at some time in their sexual lives. Deep dyspareunia has been shown to lower or cease intercourse, thus lowering self-esteem and resulting in negative effects on sexual functioning and interpersonal relationships.

A potential contributor to deep dyspareunia in women with endometriosis that is largely under-researched is the concept of central sensitization. Central sensitization is an amplification of nociceptive signaling that may result from prolonged pain causing sensitization of the dorsal horn neurons, which results in hyperalgesia (increased response to pain) and allodynia (response to pain when there normally

would not be). A recent study, comparing cross-sectional data from suspected or surgically diagnosed endometriosis patients, suggested that bladder and pelvic floor tenderness may be markers of central sensitization. However, the linkage between the indirect markers of central sensitization and the presence of central sensitization requires confirmation. This link can be assessed through validated quantitative sensory testing (QST). Likewise, the association between central sensitization and deep dyspareunia may also be confirmed through QST. QST is an objective measurement tool to determine the presence and/or degree of sensory disturbances, by detecting the alterations in nociceptive pathways. For example, a low pain-pressure threshold (i.e., increased pain sensation) at healthy unaffected areas, as measured by QST, indicates central sensitization.

---

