### Design

This study is a longitudinal, prospective cohort study, involving cases and controls. The analyses will be carried out within cases, while the controls are primarily used for troubleshooting and optimization of the QST. We will collect data prior to the test date (QST appointment) and data on the test date (for cases and controls), as well as six weeks of daily survey completion after the test date, for cases only.

Primary Outcome: Severity of deep dyspareunia

Secondary Outcomes: Severity of superficial dyspareunia, severity of non-sexual pains, sexual quality of life (EHP-30)

Main Independent Variables: Central sensitization (measured by pain-pressure threshold (PPT) determined through QST)

Study Population: The case population includes women who have consented to the Data Registry (H16-00264) and who are new or re-referred to the BC Women's Health Centre for Pelvic Pain and Endometriosis, and who have, regardless of the severity of deep dyspareunia, either: 1) previous surgical diagnosis of endometriosis or 2) current ovarian endometrioma cyst or 3) current endometriosis nodule.

Sample Size: 126 cases and 50 controls. Due to the nature of the testing in this study and the fact that participants may not benefit directly from participating in this study, it is difficult to estimate the percentage of individuals who will take part in this study. However, we estimate that it will take approximately 6 months to recruit our desired sample size of 176 participants, and we will be assessing the recruitment rate throughout the study period. At the Centre, we see approximately 300 patients meeting the criteria for this study per year.

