### **Procedures for Data Collection (after Test day)**

#### **Online Survey:**

Cases only:

- After recruitment and signing the consent form, case participants will be asked to record study data daily after their scheduled test date.
- REDCap surveys will be completed for six weeks after the test date, and data will be collected at the end of the six weeks. The data collected on the surveys for this study is shown in Appendix C.
- The data collected (shown in Appendix C), will allow for daily prospective pain scores, rather than retrospective recollections of pain scores.
- All case participants will receive daily notifications to complete the survey. Case participants will be sent one email reminder in the evening if they have not filled out the questionnaire that day. A Mental Health Crisis line number is given on the notifications in case the participant becomes distressed. At the end of the first week of entering the survey data, the participants will receive a phone call, from [name] or her delegate, to follow up on usage and any troubles or suggestions. Any problems will be addressed by [name].

Participants without email addresses will have the opportunity to complete the surveys on a printed out copy (given to them on the appointment day) and mail/bring in-person to the Centre at the end of the 6 weeks. Two weeks after the end of the study (after 6 weeks of survey entry), if the participant who completed their surveys on printed copies have not sent in their data, [name] or her delegate will call the participant to kindly remind them to mail/bring in the data.

The recruitment and procedures for this study are illustrated in Appendix A (Case) and Appendix B (Controls).

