#### Data Linking:

The Data Registry for Chronic Pelvic Pain and Endometriosis (H16-00264) collects a wide range of data from all consenting patients of the BC Women's Centre for Pelvic Pain and Endometriosis including those who undergo surgery at the clinic. Case participants in this study (Endometriosis deep dyspareunia and central sensitization) are therefore also listed in the Data Registry (they consent to both). This will allow for direct matching. A data access request will be sent to the research coordinator ([name]) to collect the case participant data from the Data Registry. The information provided to the Data Registry research coordinator for data linking includes: unique study ID, MRN, PHN, first and last name, and date of initial visit to BC Women's Health Centre. All the data from the Data Registry is being linked. This data will be placed in an encrypted excel file on the O: drive. The research coordinator will pull the appropriate information and replace the participants Data Registry REDCap ID with the unique study ID for this study and place the file back on the O: drive, where [name] or her delegate will have access to it. Data for both studies are kept on the BC Women's secure O: drive in separate password protected folders with restricted access to study team members; therefore the data transfer can be undertaken within the PHSA secure network.

Once data linkage is complete the linking spreadsheet sent to the Data Registry research coordinator will be permanently deleted as per UBC policy 85.

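### The daily deep-penetration item has no accurate answer for intercourse without deep penetration, and a 0 given on such a day looks the same as painless deep intercourse

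*Combined protocol and SAP*

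**What the plan says.** The Design section gives "Primary Outcome: Severity of deep dyspareunia" and lists superficial dyspareunia as a secondary outcome. The Background states: "Deep dyspareunia is defined as pelvic pain with deep sexual intercourse". The Data Analysis section tests the primary outcome against pain-pressure threshold (PPT) by Spearman correlation within cases.

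The daily survey in Appendix C, completed by cases for six weeks, has two intercourse items. The first asks "In the last 24 hours, how painful was deep penetration during sexual intercourse". The second asks "how painful was initial penetration (entry) during sexual intercourse". Both use the same response set, which begins "Not applicable (no intercourse), 0= no pain" and runs to 10. No completion instruction is given, and no other item asks whether intercourse or deep penetration took place.

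The Online Survey section says the diary "will allow for daily prospective pain scores, rather than retrospective recollections of pain scores". It is not the only source of sexual pain scores. The test-day questionnaire collects "score of sexual and non-sexual pains, first day of last menstrual period", and the Data Linking section adds: "All the data from the Data Registry is being linked". Nothing states which source, or which summary of daily scores, enters the primary test.

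**The concern.** The shared not-applicable code is defined by absence of intercourse. That suits the entry item. It does not suit the deep item, because intercourse can take place without deep penetration. On such a day the not-applicable label is untrue, and any number from 0 to 10 rates something that did not happen.

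The possible answers have different consequences. A blank or a wrong not-applicable code loses a day. A 0 puts the woman at the pain-free end of the scale for that day. If depth is limited because of pain, a woman with severe deep dyspareunia is then ranked with women who have none. In a rank correlation that hides the association the study is looking for, and the diary gives no way to recover the true state later. The study was sized for power 0.80, so there is little slack.

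**Working it through.** **The plan's own figure.** Data Analysis gives power 0.80, two-sided alpha 0.05 and 126 cases, based on data from 30 cases. The effect size is not stated, so 126 can only be back-solved. With n = ((1.960 + 0.842)/atanh r)² + 3, n = 126 gives r = tanh(2.802/√123) = 0.247. With a variance factor of 1.06 for Spearman it gives tanh(2.802 × √(1.06/123)) = 0.254. At r = 0.25 the two formulas give 124 and 131. The figure is plausible for r near 0.25 but cannot be verified.

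**What each answer does on a day with intercourse but no deep penetration.**
- Blank: a missing day.
- Not applicable: a missing day, detectable if the entry item has a 0–10 score that day.
- 1–10 (partial depth or expected pain): an inexact score.
- 0: identical to painless deep penetration. A high entry score beside it proves nothing, because entry can hurt when depth does not.

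**Size, on assumed inputs.** The documents give no severity distribution, no correlation and no share of women who avoid depth. Assume true severity = round(5 + 3z), clipped to 0–10, with a true Spearman correlation of about −0.27. In this model 30.8% of women score 7 or more. Let a fraction f of them be affected: f = 10%, 20% and 30% is 0.308 × f × 126 = about 4, 8 and 12 of 126 women. Power = Φ(atanh|ρ| × √((n − 3)/1.06) − 1.96). With no one affected, ρ = −0.271 and n = 126: 0.278 × 10.77 − 1.96 = 1.04, so power is 0.85.

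| Affected women are recorded as | f = 10% | f = 20% | f = 30% |
|---|---|---|---|
| Score halved (about half their episodes false zeros, averaged) | 0.82 | 0.79 | 0.75 |
| Every score 0 | 0.74 | 0.61 | 0.47 |
| Not applicable, dropped | 0.83 | 0.81 | 0.78 |

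In the all-zero row, ρ falls to −0.24, −0.20 and −0.17. In the dropped row it stays at about −0.26 to −0.27, and most of the loss comes from smaller n.

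**A second model, starting nearer the planned power.** Here the correlation is about 0.257 in size, power is about 0.81, and the affected share is taken over all women. If 10% have every score set to 0, power is 0.64 when this is unrelated to pain and 0.56 when it rises in proportion to pain. If the same 10% are dropped as not applicable, power is about 0.76. Both models agree that the damage comes from the false 0, not from the wrong not-applicable code.

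**The case against.** A reader might infer that the diary forces a false answer, and that women who avoid depth because of pain therefore enter the primary outcome as pain-free. The documents do not support that, for five reasons.

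- Nothing says the item is mandatory, so a blank is possible. Not applicable is at least as natural as 0 for something that did not happen.
- The deep item comes before the entry item, so it cannot be argued that having just scored entry pain steers her away from not applicable and towards 0.
- No section names the diary as the source of the primary outcome. Test-day or registry scores could be used. With a per-woman maximum, occasional false zeros would matter little.
- The Background says deep dyspareunia reduces or ends intercourse. It does not mention avoiding depth. A woman who stops because entry hurts has superficial dyspareunia, and her deep-pain severity is unknown.
- The largest power losses require an affected woman to score 0 on every occasion for six weeks.

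All five points stand. They make the effect conditional and limit its size. They do not supply the missing response, and they do not make a false 0 detectable.

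**Conclusion.** The gap in the response set is certain from Appendix C. Its effect on the primary result is conditional on three things the documents leave open: that the diary supplies the primary outcome, that some women answer 0 when depth did not occur, and that depth is avoided more often by women with more pain. (The second model shows that false zeros unrelated to pain also weaken the correlation, but less.) If these hold, the bias is towards no association.

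A moderate loss, from about 0.85 to 0.82–0.75, fits the halved-score case. The fall to 0.74–0.47 is an upper-end illustration and should not be quoted as the expected loss. All these figures rest on an assumed distribution, correlation and affected share. The change is worth making because it concerns how the primary construct is measured, costs little, and cannot be replaced by later analysis.

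**What to change.** In Appendix C, add to the deep-penetration item the response *Intercourse, but deep penetration did not happen*, with two reasons to tick: *because of pain or expected pain* and *other reason*. Keep the existing not-applicable code for days without intercourse, and state on the form that 0 applies only if deep penetration took place.

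In the analysis, do not score the new category as 0. Use true 0–10 answers in the main Spearman analysis, and add a sensitivity analysis that ranks pain-related avoidance at the severe end. Name the source and per-woman summary of the primary outcome, since these decide how far the point matters.

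For diaries already completed, flag days with not applicable on depth but a 0–10 entry score. False zeros in those diaries cannot be found. The test-day question's responses are not shown in the documents, so change it only if it has the same gap.

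The cost is one REDCap response option, a minor ethics amendment and a slightly longer daily item. Diaries completed before the change, including any from the 30 cases used for the power analysis, will lack the category, so the data will mix two versions of the item.
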